Study logistics	

1. Identify patient with suspected relapse

2. Trial discussed, consent obtained and bone marrow performed

3. If MRD positive or morphologic relapse, stop immunosuppression within a week of biopsy results

4. If no evidence of GVHD in 2 weeks after stopping immunosuppression, start Daratumumab.

5. Daratumumab may be given as outpatient or inpatient depending on treating physician discretion.

6. Patient will be seen prior to every Daratumumab dose and assessment for GVHD will be done

7. Plan bone marrow biopsy after doses 3 and before dose 4.

8. Administer DLI between weeks 3-5.

9. Resume weekly Dara weeks 6-8

Date of protocol: 10/14/2020

IRB Approval Date: 11/24/2020

Version of protocol: 7

IND number: 139015

Institutional protocol number: OSU 17102

	10. Bone marrow biopsy after week 8
Study Objectives – Phase I	
Primary Objectives:
 
1. Phase I: To determine the maximum tolerated dose (MTD) of Daratumumab and escalating doses of donor lymphocyte infusions (DLI) in post-HCT patients with relapsed AML and MDS transformed to AML.
 
2. Phase II: To evaluate overall response rate to Daratumumab and DLI by week 8 in patients with post-HCT relapsed AML and MDS
 
Secondary Objectives:
 

1. To assess overall response rates in MRD positive patients and in patients with overt morphological relapse

2. To assess MRD conversion rates from MRD positive to MRD negative.

3. To determine the post-relapse 6-month OS rates of patients with relapsed AML and MDS following allo-HSCT who are treated with Daratumumab

4. To determine the rates of GVHD (both grades II-IV and III-IV) and autoimmune side effects of Daratumumab by 3 months.

5. To determine the post-relapse 6-month PFS rates of patients with relapsed AML and MDS following allo-HSCT who are treated with Daratumumab

Safety Assessment	Physical examination, electrocardiogram (ECG), clinical laboratory tests (hematology, blood chemistries, urinalysis, prothrombin time [PT], activated partial thromboplastin time [APTT]), anti-drug antibody (ADA), cytokine/inflammatory factor levels, vital signs, and adverse event/toxicity assessment.
Efficacy Assessment	Standard response assessment as defined for AML, duration of response, and overall survival/PFS.

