## 8 STUDY POPULATION

### 8.1 INCLUSION CRITERIA

1. Age  $\geq$  18 years
2. AML or MDS relapse following Allo-HSCT (Morphological relapse, or MRD positive by flow cytometry, cytogenetics, and molecular mutations)
3. Patients who received a 10/10 HLA-matched allogeneic HCT either from sibling donors or unrelated donors or at least a 5/10 haploidentical transplant for Dose level 2 and 3
4. Patients with R/R AML must not be candidates for available therapies known to be effective for treatment of their AML.
5. For patients in Dose level 1 (Daratumumab only), relapsed refractory AML patients who have previously not received an allogeneic HCT are eligible.
6. Engraftment must have occurred as defined by platelet (PLT) count  $> 20,000/\mu\text{L}$  and ANC  $\geq 0.5$
7. ECOG performance status  $< 3$
8. Creatinine clearance  $> 40 \text{ ml/min}$  (Calculated or measured)
9. Aspartate aminotransferase (AST)  $< 3 \times$  upper limit of normal (ULN), alanine aminotransferase (ALT)  $< 3 \times$  ULN, and total bilirubin  $< 1.5 \times$  ULN
10. Off calcineurin inhibitors for at least 2 weeks
11. Prednisone dose  $\leq 20 \text{ mg/day}$ .
12. Patients with proliferative disease can be cytoreduced with cytotoxic chemotherapy at investigator's discretion, but there should be at least a 14 day window between start of cytoreductive therapy and start of Daratumumab
13. Blast count  $< 20 \text{ K/day}$  (hydrea use is allowed)
14. Patient willing to agree to study-related research marrows
15. Female patients of childbearing potential who are sexually active must be willing to use an effective barrier method of birth control to avoid pregnancy during the study and for a minimum of 3 months after stopping study treatment
16. Male patients with partners of childbearing potential who are sexually active must be willing to use an effective barrier method of birth control to avoid pregnancy during the study and for a minimum of 3 months after stopping study treatment

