## 10 MANAGEMENT OF CLINICAL EVENTS

### 10.1 CYTOPENIAS

Bone marrow biopsies will be done at time of consent, prior to DLI and at week 8. Additional Bone marrow biopsies can be done at any time at discretion of treating physician. If bone marrow shows persistent disease, cytopenias would be attributed to persistent leukemia.

Transfusions will follow institutional guidelines which typically are to keep Hgb > 7gm/dL and platelet (PLT) count more than 10K/ $\mu$ l.

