#### 12.1.3 STUDY RELATED PROCEDURES AND STUDY CALENDAR

	Screening a	Pre-1 st Dose Daratumumab	Post-1 st Dose Daratumumab	Week 2	Week 3	Week 4	Week 5	Week 6	Week 7	Week 8	Long Term Follow-up
		Day 1	Day 3 or 4	Day 8	Day 15	Day 22	Day 29	Day 36	Day 43	Day 50	Day 57-71
Informed Consent	X										
Medical history	X										
Physical Exam & Vital Signs	X	X	X	X	X	X	X	X	X	X	
Pregnancy Test (if applicable)	X										
Medication Record	X		X	X	X	X	X	X	X	X	
Performance Status	X		X	X	X	X	X	X	X	X	
Blood Draw (Complete Blood Count)	X	X	X	X	X	X	X	X	X	X	
Blood Draw (Complete Metabolic Panel)	X		X	X	X	X	X	X	X	X	
GVHD Assessment	X	X	X	X	X	X	X	X	X	X	
Donor Lymphocyte Infusion (DLI)						X					
Adverse Event Monitoring	X	X	X	X	X	X	X	X	X	X	
Bone Marrow Biopsy	X					(Pre-DLI) X					X
Research Bone Marrow samples (3 green tops of 6 ml each)	X					X					X
Research blood samples (2 green tops(6 ml each) and one red top (6 ml))	X	X	X	x	X	X	x	X	X	x	

a Screening window is 28 days.

The bone marrow biopsy at week 4 can be done at week 3, but it has to be done before the DLI. So, if the DLI can be arranged at week 4, then the marrow will be done week 3. For patients deemed eligible to receive maintenance therapy, the following procedures will be performed.

Daratumumab will be administered if PLT count is > 100K and ANC> 500.

Date of protocol: 10/14/2020

IRB Approval Date: 11/24/2020

Version of protocol: 7

IND number: 139015

Institutional protocol number: OSU 17102

Week b	Start of Daratumumab Maintenance a													
	Week 9	Week 11	Week 13	Week 15	Week 17	Week 19	Week 21	Week 23	Week 25	Week 29	Week 33	Week 37	Week 41	Week 45
CBC	x	x	x	x	x	x	x	x	x	x	x	x	x	x
Vital signs	x	x	x	x	x	x	x	x	x	x	x	x	x	x
GVHD assessment	x	x	x	x	x	x	x	x	x	x	x	x	x	x
Performance status	x	x	x	x	x	x	x	x	x	x	x	x	x	x
Adverse event monitoring	x	x	x	x	x	x	x	x	x	x	x	x	x	x

a) Daratumumab maintenance, a schedule of 16mg/kg every 2 weeks for 16 (8 doses) weeks and then monthly for 6 months will be given.

b) Daratumumab can be given +/- 3 days but there has to be a week interval between doses.

marrow during Daratumumab maintenance is at the discretion of the physician and will be considered standard of care.

Date of protocol: 10/14/2020  
Version of protocol: 7  
IND number: 139015  
Institutional protocol number: OSU 17102

IRB Approval Date: 11/24/2020

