### 16.2 Analysis methods:

Analysis datasets:

Efficacy sets: All evaluable patients will be included in the analysis of the primary endpoint. The term evaluable is defined as any eligible patient who receives at least one dose of Daratumumab, does not withdraw consent, and is evaluated for response week 8; patients who fail to have a week-8 assessment due to early progression, death or toxicity will also be considered evaluable for response and categorized as non-responders. Patients who fail to have a week-8 assessment for other reasons (e.g., refusal due to travel constraints) will be considered unevaluable and will not be included in the denominator when calculating ORR rate.

Safety sets: The safety analysis dataset will include all eligible patients who receive one dose of daratumumab.

The adverse events will be examined and worst grade adverse events will be recorded for each patient and summarized by type, severity, and attribution (if possible) using NCI CTCAE version 4 criteria. Tolerability of the regimen will be assessed by summarizing the number of patients who require dose modifications and/or dose delays. In addition, we will also capture the proportion of patients who go off treatment due to adverse events or even those who refuse further treatment for lesser toxicities that inhibit their willingness to continue participation on the trial. All patients who have received at least one dose of daratumumab will be evaluable for toxicity and tolerability.

The primary endpoint of phase II is to evaluate overall response rates (ORR) to the combination of Daratumumab and DLI. The ORR will be defined as complete remission (CR), complete remission with incomplete marrow recovery (CRi), partial remission (PR) and morphological leukemia free

Date of protocol: 10/14/2020

IRB Approval Date: 11/24/2020

Version of protocol: 7

IND number: 139015

Institutional protocol number: OSU 17102

state (MLFS). The proportion of patients achieving ORR among efficacy sets will be calculated and 95% confidence interval will be estimated. In addition, the ORR among patients who received at least 3 doses of Daratumumab and DLI will be calculated as well. The ORR rate among MRD positive patients and patients with overt morphological relapse will be estimated as well. The MRD conversion rate from MRD positive to MRD negative, and the 3-month GVHD rate (both grade II-IV and III-IV) will be similarly analyzed.

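### Responses due wholly or partly to pre-study cytotoxic chemotherapy could count toward the 6-of-25 rule, and 16.2 has no analysis that separates them

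*Combined protocol and SAP*

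**What the plan says.** **Cytoreduction.** Section 8.1 (criterion 12; criterion 13 in the synopsis) states: "Patients with proliferative disease can be cytoreduced with cytotoxic chemotherapy at investigator's discretion". It sets no regimen, intensity or cycle limit. The only timing condition is that "there should be at least a 14 day window between start of cytoreductive therapy and start of Daratumumab". The next criterion adds that "hydrea use is allowed".

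**Marrow timing.** Section 10.1 states: "Bone marrow biopsies will be done at time of consent, prior to DLI and at week 8". The calendar in 12.1.3 agrees. It has a marrow at screening, one before DLI and one in the Day 57-71 column, with none on Day 1. A footnote adds: "Screening window is 28 days". The study logistics in the synopsis begin with "Trial discussed, consent obtained and bone marrow performed", then the stopping of immunosuppression, then "If no evidence of GVHD in 2 weeks after stopping immunosuppression, start Daratumumab". Sections 10.1 and 12.2 allow further marrows at the physician's discretion.

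**Endpoint.** Section 16.2 reads "The ORR will be defined as complete remission (CR), complete remission with incomplete marrow recovery (CRi), partial remission (PR) and morphological leukemia free" state. The efficacy set is eligible patients with at least one daratumumab dose and a week-8 evaluation. Early progression, death or toxicity without that evaluation counts as non-response. The section names no reference marrow for response, gives no rule for a patient already in response at dose 1, and plans no analysis by prior cytoreduction.

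**Decision rule.** Section 16 tests 10% against 30% in 25 patients and rejects the null at 6 or more responders.

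**The concern.** With no control arm, the 10% null is the only thing the observed ORR is compared with, and section 16 states that null for daratumumab plus DLI without mentioning cytoreduction. A patient could start chemotherapy two weeks before dose 1, have blasts reduced or cleared by it, and be recorded as a responder at week 8. Nothing collected under the schedule would show how much of that response preceded daratumumab. The next scheduled marrow, before DLI, follows about three daratumumab doses and cannot separate the two effects.

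What is at stake is the attribution of a positive result. A few such responses can decide whether the count reaches 6, and the planned tables would not show that this had happened.

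**Working it through.** **1. Can the sequence occur?** The screening window is 28 days and the minimum interval is 14 days, so cytoreduction can fit between the screening marrow and dose 1. The logistics also put at least 2 weeks between stopping immunosuppression, which follows the marrow result, and dose 1. If chemotherapy instead starts before consent, the screening marrow may follow it, but nothing requires that marrow to show the chemotherapy's effect. The gap exists in either order.

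**2. The plan's own figures.** Inputs from section 16: n = 25, rejection at 6 or more, null 0.10, alternative 0.30.
- P(Bin(25, 0.10) ≥ 6) = 0.0334
- P(Bin(25, 0.30) ≥ 6) = 0.8065

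The smallest n with exact one-sided error at most 0.05 and power at least 0.80 is 25, so the design reproduces. There is little slack: the error passes 0.05 once a common response rate under the null reaches about 11.0% instead of 10%.

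**3. Effect of chemotherapy responses.** The documents give neither the number cytoreduced (m) nor the response rate to chemotherapy alone (q). Both are assumptions here. Take the regimen at its null, with m patients responding at rate q and the other 25 − m at 0.10:

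P(false positive) = P(Bin(m, q) + Bin(25 − m, 0.10) ≥ 6)

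For m = 1 and q = 0.20, this is 0.20 × P(Bin(24, 0.10) ≥ 5) + 0.80 × P(Bin(24, 0.10) ≥ 6) = 0.20 × 0.0851 + 0.80 × 0.0277 = 0.039.

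| m of 25 | q = 0.20 | q = 0.30 | q = 0.40 |
|---|---|---|---|
| 0 | 0.033 | 0.033 | 0.033 |
| 1 | 0.039 | 0.045 | 0.051 |
| 2 | 0.046 | 0.059 | 0.074 |
| 3 | 0.053 | 0.076 | 0.105 |
| 5 | 0.069 | 0.121 | 0.188 |

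**4. Dependence on the model.** Step 3 treats q as the whole response rate of a cytoreduced patient. If the chemotherapy response instead comes on top of the 10%, and a share f of patients is cytoreduced, the null rate becomes 0.10 + 0.90 × f × q. For f = 0.20 (5 of 25) and q = 0.20 it is 0.10 + 0.90 × 0.04 = 0.136, and the error is 0.114 against 0.069 in the table. The direction is the same. The size depends on assumptions that the documents cannot settle.

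**The case against.** The strongest reply is that exposure may be small and its effect on a week-8 response weaker than it first appears. Four parts of that reply stand, each against a reading that a reader might be tempted to make.

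- **That chemotherapy responses do count.** The documents permit the order marrow, chemotherapy, daratumumab but do not fix it. Cytoreduction appears only among the eligibility criteria, and the logistics do not mention it. One case report form is titled for screening or D1, which leaves a Day 1 marrow possible although none is scheduled. The supported statement is that such responses could count.
- **That response is judged against a pre-chemotherapy marrow.** Section 16.2 names no reference marrow at all, so this cannot be read from the text.
- **That the regimen contributes nothing to these responses.** The final marrow is at Day 57-71. Day 57 is 56 days after Day 1, so chemotherapy began at least 14 + 56 = 70 days before it. A patient still in response then has usually had several daratumumab doses and perhaps DLI. Early progression or death counts as non-response, and rapid progressors leave the trial (7.1, 16.3). Attribution is therefore uncertain, not nil. The filter is imperfect, since the objective in 5.1 speaks of response by week 8.
- **That the inflation is large.** Section 8.1 requires that relapsed or refractory patients not be candidates for therapies known to be effective. Section 4.1 reports a median survival of 51 days after chemotherapy in one series. That is survival rather than response, but it argues against assuming a high q. With one or two cytoreduced patients the error is 3.9-7.4%.

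None of this closes the gap. No section prevents a chemotherapy response from counting, and no planned analysis would reveal it.

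**Conclusion.** The point holds as a gap in the analysis plan, not as a demonstrated bias. Chemotherapy may start as little as 14 days before daratumumab, no marrow is required between the two, and 16.2 counts all responses alike. Under the assumed 20-40% response in cytoreduced patients, the false-positive rate of the 6-of-25 rule goes from 3.3% to between 3.9% (one patient, 20%) and 18.8% (five patients, 40%). The true size is unknown. If nobody is cytoreduced, the rate stays at 3.3%. The point merits a change because the result excluding these patients affects what the trial can conclude about the regimen and costs little to report.

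A reader might infer that the screening marrow should be moved to after cytoreduction, or that cytoreduced patients without documented active disease should automatically be non-responders. The documents do not support either step. The logistics use the initial marrow to establish relapse or MRD and to trigger the stopping of immunosuppression. MRD-positive patients are also eligible, so a requirement of active disease would be undefined for them and could bias the ORR downward.

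**What to change.** In 16.2:

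1. Prespecify the ORR with an exact 95% CI, with and without patients who received cytotoxic cytoreduction between relapse and the first daratumumab dose. Identify them from the AML baseline history form, which already records dates for 7+3, HiDAC, decitabine, azacitidine and hydrea, and the date of the last chemotherapy dose.
2. Require that any conclusion of activity attributed to daratumumab plus DLI be stated together with the result excluding these patients.
3. Where a marrow was in any case taken after cytoreduction and before dose 1, use it as the reference for response. In that analysis, do not credit a patient who already met the same response category on it.

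No added or re-timed marrow is required, and the use of cytoreduction is unchanged.

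**Cost.** One extra table, a smaller denominator and wider interval in the sensitivity analysis, and a possibly lower ORR. The 6-responder threshold does not carry over to a reduced set. With 3 of 25 removed, for example, 6 or more of 22 has exact error 0.018 and power 0.687 at 30%. The restricted result is best read as an estimate with its interval, not as a second test.

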### 8.2 EXCLUSION CRITERIA

1. No demonstrable evidence of donor chimerism ( $< 55$  donor CD3 or CD33 chimerism)
2. Patients with a molecular mutation without chromosomal abnormalities or declining chimerisms (MRD status must be verified by surface marker and mutational analyses)
3. Active graft-versus-host disease (GVHD) grades I-IV; prior acute GVHD could have occurred but resolved at time of initiation of Daratumumab
4. Extensive chronic GVHD requiring ongoing immunosuppression with calcineurin inhibitors or more than 20 mg of prednisone
5. Patients with FLT3+ AML or blast crisis CML who have not yet received post-transplant TKI therapy

6. Active CNS or testicular disease
7. Subject is:
  - 7.2 seropositive for human immunodeficiency virus (HIV)
  - 7.3 seropositive for hepatitis B (defined by a positive test for hepatitis B surface antigen [HBsAg]).  
Subjects with resolved infection (ie, subjects who are HBsAg negative but positive for antibodies to hepatitis B core antigen [anti-HBc] and/or antibodies to hepatitis B surface antigen [anti-HBs]) must be screened using real-time polymerase chain reaction (PCR) measurement of hepatitis B virus (HBV) DNA levels. Those who are PCR positive will be excluded. EXCEPTION: Subjects with serologic findings suggestive of HBV vaccination (anti-HBs positivity as the only serologic marker) AND a known history of prior HBV vaccination, do not need to be tested for HBV DNA by PCR.
8. seropositive for hepatitis C (except in the setting of a sustained virologic response [SVR], defined as aviremia at least 12 weeks after completion of antiviral therapy).
9. Patients must not have chronic obstructive pulmonary disease with a forced expiratory volume in 1 second (FEV1) < 50% of predicted normal. FEV1 is required for patients suspected of having chronic obstructive pulmonary disease and are not eligible if FEV1 is < 50% of predicted normal.
10. Patients must not have moderate or severe persistent asthma within the past 2 years and must not have currently uncontrolled asthma of any classification.
11. Active autoimmune disease prior to transplant
12. Female patients of childbearing potential who are sexually active and unwilling to use an effective barrier method of birth control to avoid pregnancy during the study and for a minimum of 3 months after study treatment.
13. Male patients with partners of childbearing potential who are sexually active and unwilling to use an effective barrier method of birth control to avoid pregnancy during the study and for a minimum of 3 months after study treatment
14. Concurrent use of any other investigational drugs

## 9 DARATUMUMAB ADMINISTRATION

Daratumumab will be dosed at 16mg/kg following guidelines provided in package insert. For management of infusion-related toxicities, see 9.2.

### 9.1 RECOMMENDED CONCOMITANT MEDICATIONS

#### 9.1.1 Pre-infusion Medication

Administer pre-infusion medications to reduce the risk of infusion reactions to all patients 1-3 hours prior to every infusion of Daratumumab per OSU guidelines

#### 9.1.2 Post-infusion Medication

Administer post-infusion medication to reduce the risk of delayed infusion reactions to all patients as follows according to OSU guidelines.

In addition, for any patients with a history of chronic obstructive pulmonary disease, consider prescribing post-infusion medications such as short and long-acting bronchodilators, and inhaled corticosteroids. Following the first four infusions, if the patient experiences no major infusion reactions, these additional inhaled post-infusion medications may be discontinued.

Date of protocol: 10/14/2020

IRB Approval Date: 11/24/2020

Version of protocol: 7

IND number: 139015

Institutional protocol number: OSU 17102

## 9.2 DARATUMUMAB INFUSION RELATED REACTIONS

For infusion reactions of any grade/severity, immediately interrupt the DARATUMUMAB infusion and manage symptoms. Management of infusion reactions may further require reduction in the rate of infusion, or treatment discontinuation of DARATUMUMAB as outlined below.

- Grade 1-2 (mild to moderate): Once reaction symptoms resolve, resume the infusion at no more than half the rate at which the reaction occurred. If the patient does not experience any further reaction symptoms, infusion rate escalation may resume at increments and intervals as clinically appropriate up to the maximum rate of 200 mL/hour.
- Grade 3 (severe): Once reaction symptoms resolve, consider restarting the infusion at no more than half the rate at which the reaction occurred. If the patient does not experience additional symptoms, resume infusion rate escalation at increments and intervals as clinically appropriate. Repeat the procedure above in the event of recurrence of Grade 3 symptoms. Permanently discontinue DARATUMUMAB upon the third occurrence of a Grade 3 or greater infusion reaction.
- Grade 4 (life threatening): Permanently discontinue Daratumumab treatment.

## 9.3 DONOR LYMPHOCYTE INFUSION

Donor lymphocytes are typically infused as outpatient according to institutional guidelines. To allow for scheduling ease, DLI will be infused within 72 hrs. after the daratumumab dose, anytime between week 3-4. .

## 9.4 CRITERIA TO BE MET BEFORE EACH DOSE OF DARATUMUMAB

Patients need to be evaluated with documentation of the following before starting each dose of Daratumumab:

1. Patient is hemodynamically stable without concern for active infection
2. No evidence of active GVHD
3. Prednisone dose is  $\leq$  20mg/day.

